9.3 Data management

Each institution will ensure the necessary compliance with local data protection, storage and archiving, and patient privacy laws and regulations and will obtain all permission necessary to conduct this study. In the Netherlands, completely anonymised data will be obtained from the Dutch Foundation for Pharmaceutical Statistics (SFK) for which no separate ethical approval is necessary.

In Denmark no ethical approval is needed since the study is purely registry based. Permission from our Data Protection Agency will be obtained.

9.4 Quality control

The drafts of the study plan and protocol and final versions will be overseen by the lead researcher. There will be administrative support to ensure smooth running of the project and five steering group meetings, roughly spaced throughout the project.

The lead researcher is experienced in supervising as well as experienced in the proposed

methodology, specific methods and topic of decision making. The wider consortium have previously worked together successfully on tenders for the EMA.

9.5 Limitations of the research methods

Women in the SFK who receive an anticoagulant treatment (DOAC or VKA) are women who survived a thrombosis. Women who died (with a worse prognosis) will not have a treatment prescription and are therefore not identified as cases in this study.

Because we are relying on the anticoagulant treatment as a proxy for women having a VTE, the cases are not confirmed cases, since the real diagnostic criteria for Deep vein Thrombosis (Doppler ultrasonography) and Pulmonary Embolism (ventilation perfusion lung scan, spiral computed tomography, or angiogram) is not assessed.

In Denmark all executed prescriptions are registered in the Danish National Prescription Registry. Combined oral contraceptives are prescription medications and the registration is an automated process, so the data validity is considered high. Regarding VTE occurrence data is obtained from the National Registry of Patients. This registry is automatically updated with all diagnosis codes from Danish Hospital contacts, so as for the Netherlands VTEs that might miss in this project are those with fatal disease that do not attend hospital.

10. Protection of human subjects

No ethical approval is needed.

11. Plans for disseminating and communicating study results

Results from WP1-6 will be combined for the final report for the EMA and in the manuscript for submission for publication in an academic journal.

The abstract of the paper can be submitted for conferences.

12. References

1. Value of the ventilation/perfusion scan in acute pulmonary embolism. Results of the prospective investigation of pulmonary embolism diagnosis (PIOPED). The PIOPED Investigators. JAMA. 1990;263(20):2753-9.

3. [name] A, Helmerhorst FM, Vandenbroucke JP, Doggen CJ, Rosendaal FR. The venous thrombotic risk of oral contraceptives, effects of oestrogen dose and progestogen type: results of the MEGA case-control study. *BMJ*. 2009;339:b2921.

ENCePP Checklist for Study Protocols (Revision 3)

Adopted by the ENCePP Steering Group on 01/07/2016

The [European Network of Centres for Pharmacoepidemiology and Pharmacovigilance \(ENCePP\)](#) welcomes innovative designs and new methods of research. This Checklist has been developed by ENCePP to stimulate consideration of important principles when designing and writing a pharmacoepidemiological or pharmacovigilance study protocol. The Checklist is intended to promote the quality of such studies, not their uniformity. The user is also referred to the [ENCePP Guide on Methodological Standards in Pharmacoepidemiology](#), which reviews and gives direct electronic access to guidance for research in pharmacoepidemiology and pharmacovigilance.

For each question of the Checklist, the investigator should indicate whether or not it has been addressed in the study protocol. If the answer is "Yes", the section number of the protocol where this issue has been discussed should be specified. It is possible that some questions do not apply to a particular study (for example, in the case of an innovative study design). In this case, the answer 'N/A' (Not Applicable) can be checked and the "Comments" field included for each section should be used to explain why. The "Comments" field can also be used to elaborate on a "No" answer.

This Checklist should be included as an Annex by marketing authorisation holders when submitting the protocol of a non-interventional post-authorisation safety study (PASS) to a regulatory authority (see the [Guidance on the format and content of the protocol of non-interventional post-authorisation safety studies](#)). The Checklist is a supporting document and does not replace the format of the protocol for PASS as recommended in the Guidance and Module VIII of the Good pharmacovigilance practices (GVP).

Study title: Study of utilization of combined hormonal contraceptives in Europe

Study reference number: EMA/49122/2016

Section 1: Milestones	Yes	No	N/A	Section Number
1.1 Does the protocol specify timelines for				
1.1.1 Start of data collection ¹				6.milestones
1.1.2 End of data collection ²				6.milestones
1.1.3 Study progress report(s)				
1.1.4 Interim progress report(s)				
1.1.5 Registration in the EU PAS register				
1.1.6 Final report of study results.				6.milestones

¹ Date from which information on the first study is first recorded in the study dataset or, in the case of secondary use of data, the date from which data extraction starts.

² Date from which the analytical dataset is completely available.

Comments:

--

Section 2: Research question	Yes	No	N/A	Section Number
2.1 Does the formulation of the research question and objectives clearly explain:				
2.1.1 Why the study is conducted? (e.g. to address an important public health concern, a risk identified in the risk management plan, an emerging safety issue)				7
2.1.2 The objective(s) of the study?				8
2.1.3 The target population? (i.e. population or subgroup to whom the study results are intended to be generalised)				4
2.1.4 Which hypothesis(-es) is (are) to be tested?				7
2.1.5 If applicable, that there is no a priori hypothesis?				

Comments:

--

Section 3: Study design	Yes	No	N/A	Section Number
3.1 Is the study design described? (e.g. cohort, case-control, cross-sectional, new or alternative design)				9.1
3.2 Does the protocol specify whether the study is based on primary, secondary or combined data collection?				9.2 (methods per WP)
3.3 Does the protocol specify measures of occurrence? (e.g. incidence rate, absolute risk)				9.2 (WP 1-3)
3.4 Does the protocol specify measure(s) of association? (e.g. relative risk, odds ratio, excess risk, incidence rate ratio, hazard ratio, number needed to harm (NNH) per year)				9.2 (WP 4-6)
3.5 Does the protocol describe the approach for the collection and reporting of adverse events/adverse reactions? (e.g. adverse events that will not be collected in case of primary data collection)				

Comments:

Ad 3.5 We will make use of existing data registries

Section 4: Source and study populations	Yes	No	N/A	Section Number
4.1 Is the source population described?				9.2 (study pop. per WP)
4.2 Is the planned study population defined in terms of:				
4.2.1 Study time period?				9.2
4.2.2 Age and sex?				9.2
4.2.3 Country of origin?				9.2

Section 4: Source and study populations	Yes	No	N/A	Section Number
4.2.4 Disease/indication?				9.2
4.2.5 Duration of follow-up?				9.2
4.3 Does the protocol define how the study population will be sampled from the source population? (e.g. event or inclusion/exclusion criteria)				9.2

Comments:

--

Section 5: Exposure definition and measurement	Yes	No	N/A	Section Number
5.1 Does the protocol describe how the study exposure is defined and measured? (e.g. operational details for defining and categorising exposure, measurement of dose and duration of drug exposure)				9.2 (analysis per WP)
5.2 Does the protocol address the validity of the exposure measurement? (e.g. precision, accuracy, use of validation sub-study)				
5.3 Is exposure classified according to time windows? (e.g. current user, former user, non-use)				Page 9 (population)
5.4 Is exposure classified based on biological mechanism of action and taking into account the pharmacokinetics and pharmacodynamics of the drug?				9.2

Comments:

Ad 5.2 exposure is registered in existing databases

Section 6: Outcome definition and measurement	Yes	No	N/A	Section Number
6.1 Does the protocol specify the primary and secondary (if applicable) outcome(s) to be investigated?				9.2 (specified per WP)
6.2 Does the protocol describe how the outcomes are defined and measured?				9.2 (analysis per WP)
6.3 Does the protocol address the validity of outcome measurement? (e.g. precision, accuracy, sensitivity, specificity, positive predictive value, prospective or retrospective ascertainment, use of validation sub-study)				
6.4 Does the protocol describe specific endpoints relevant for Health Technology Assessment? (e.g. HRQoL, QALYs, DALYS, health care services utilisation, burden of disease, disease management)				

Comments:

--

Section 7: Bias	Yes	No	N/A	Section Number
7.1 Does the protocol describe how confounding will be addressed in the study?				9.2 (stratification)
7.1.1. Does the protocol address confounding by indication if applicable?				
7.2 Does the protocol address:				
7.2.1. Selection biases (e.g. healthy user bias)				
7.2.2. Information biases (e.g. misclassification of exposure and endpoints, time-related bias)				9.5
7.3 Does the protocol address the validity of the study covariates?				9.5

Comments:

Ad 7.1 This is a descriptive analysis

Section 8: Effect modification	Yes	No	N/A	Section Number
8.1 Does the protocol address effect modifiers? (e.g. collection of data on known effect modifiers, sub-group analyses, anticipated direction of effect)				

Comments:

Section 9: Data sources	Yes	No	N/A	Section Number
9.1 Does the protocol describe the data source(s) used in the study for the ascertainment of:				
9.1.1 Exposure? (e.g. pharmacy dispensing, general practice prescribing, claims data, self-report, face-to-face interview)				9.2 (per WP)
9.1.2 Outcomes? (e.g. clinical records, laboratory markers or values, claims data, self-report, patient interview including scales and questionnaires, vital statistics)				9.2 (per WP)
9.1.3 Covariates?				9.2 (per WP)
9.2 Does the protocol describe the information available from the data source(s) on:				
9.2.1 Exposure? (e.g. date of dispensing, drug quantity, dose, number of days of supply prescription, daily dosage, prescriber)				
9.2.2 Outcomes? (e.g. date of occurrence, multiple event, severity measures related to event)				
9.2.3 Covariates? (e.g. age, sex, clinical and drug use history, co-morbidity, co-medications, lifestyle)				9.2 (per WP)
9.3 Is a coding system described for:				
9.3.1 Exposure? (e.g. WHO Drug Dictionary, Anatomical Therapeutic Chemical (ATC) Classification System)				9.1
9.3.2 Outcomes? (e.g. International Classification of Diseases (ICD)-10, Medical Dictionary for Regulatory Activities (MedDRA))				9.1

Section 9: Data sources	Yes	No	N/A	Section Number
9.3.3 Covariates?				9.2 (per WP)
9.4 Is a linkage method between data sources described? (e.g. based on a unique identifier or other)				

Comments:

--

Section 10: Analysis plan	Yes	No	N/A	Section Number
10.1 Is the choice of statistical techniques described?				9.2 (per WP)
10.2 Are descriptive analyses included?				9.2 (per WP)
10.3 Are stratified analyses included?				9.2 (per WP)
10.4 Does the plan describe methods for adjusting for confounding?				
10.5 Does the plan describe methods for handling missing data?				
10.6 Is sample size and/or statistical power estimated?				Page 10 (study size)

Comments:

--

Section 11: Data management and quality control	Yes	No	N/A	Section Number
11.1 Does the protocol provide information on data storage? (e.g. software and IT environment, database maintenance and anti-fraud protection, archiving)				
11.2 Are methods of quality assurance described?				9.4
11.3 Is there a system in place for independent review of study results?				

Comments:

--

Section 12: Limitations	Yes	No	N/A	Section Number
12.1 Does the protocol discuss the impact on the study results of:				
12.1.1 Selection bias?				
12.1.2 Information bias?				
12.1.3 Residual/unmeasured confounding? (e.g. anticipated direction and magnitude of such biases, validation sub-study, use of validation and external data, analytical methods)				

Section 12: Limitations	Yes	No	N/A	Section Number
12.2 Does the protocol discuss study feasibility? (e.g. study size, anticipated exposure, duration of follow-up in a cohort study, patient recruitment)				Page 10

Comments:

This study uses large pharmacy databases, civil registration systems, and primary care data.

Section 13: Ethical issues	Yes	No	N/A	Section Number
13.1 Have requirements of Ethics Committee/ Institutional Review Board been described?				10
13.2 Has any outcome of an ethical review procedure been addressed?				
13.3 Have data protection requirements been described?				9.3

Comments:

Section 14: Amendments and deviations	Yes	No	N/A	Section Number
14.1 Does the protocol include a section to document amendments and deviations?				5

Comments:

Section 15: Plans for communication of study results	Yes	No	N/A	Section Number
15.1 Are plans described for communicating study results (e.g. to regulatory authorities)?				11
15.2 Are plans described for disseminating study results externally, including publication?				11

Comments:

Name of the main author of the protocol: [name]

Date: 09/10/2017

Signature: _____

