Delivery of manuscript	01-05-2018

7. Rationale and background

Venous thromboembolism (VTE) in young women is rare, with an annual incidence of approximately 2-5 per 10 000 women (6). An increased risk of VTE associated with oral contraceptive use has long been established and while the absolute risk of VTE in young women is low, the fact that millions of women worldwide are using oral contraceptives indicates that these preparations are responsible for a large number of cases of VTE

(3, 7-11). Several large studies including a review in 2013 by the European Medicines Agency (EMA) concluded that the risk of VTE associated with hormonal contraceptive preparations which contained gestodene, desogestrel, or drospirenone was increased compared with hormonal contraceptive preparations containing levonorgestrel (1, 5, 12, 13).

After the publication of the review by the EMA, the European Commission adopted on 16 2014, a legally binding decision to update the product information of all combined hormonal contraceptives (CHC) throughout the European Union. This included information to patients: awareness of factors that increase the risk of VTE and information to health care professionals: the type of CHC with the lowest VTE risk (levonorgestrel, norethisterone, or norgestimate) and the fact that CHC are contraindicated in the presence of one serious or multiple risk factors for VTE. It is currently unknown whether the publication of this review led to a change in prescription patterns and a subsequent change in the incidence of VTE in young women.

The aim of this study is therefore to investigate the CHC utilisation and prescribing patterns in a sample of Three European Union Member states (Denmark, United Kingdom, and the Netherlands) in a time period including the completion of the 2013 review and implementation of the resulting recommendations and to estimate any changes in the incidence of VTE between the two periods specified.

This study will provide evidence regarding the necessity of the recommendation to use safer oral contraceptive preparations, as it will show whether the implementation of the recommendation was successful and whether it actually affected the incidence of VTE in the target population.

8. Research question and objectives

Was there a change in CHC prescribing patterns between the periods January 2012 – January 2014 and February 2014 – December 2015 and, if so, was there a subsequent change in the incidence rate of VTE?

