Medication use in the SFK database will be used to approximate the occurrence of VTE by using the first dose of oral anticoagulant, which, in case of DOAC use is specific for VTE or the duration of treatment with Vitamin K antagonists. Incidence of VTE is calculated by following the new users of CHC within each calendar window until they experience a VTE, or up to one year.

We will calculate the incidence among the new users of oral contraceptives in general and per type of oral contraceptive (different types and grouped by generation (second, third and newer generations)).

Analysis

We will tabulate the estimates of the annual incidence of VTE including 95% confidence intervals for each calendar window of the study period.

From segmented regression analysis (WP1), we will obtain information on a potential change in the proportion of initiators of each generation of CHC between January 2012-January 2014 and February 2014- December 2015. Since we have information about the prescription patterns among new users, we can assess whether the changes observed in the proportions of each generation is associated with changes in the incidence rate of VTE in women initiating oral contraceptive use.

Furthermore, we can study the changes in the incidence of VTE within users of different types (and generations) of oral contraceptives. A change in this incidence over time, may indicate that certain preparations are prescribed to low/high risk individuals.

Because we have information about the age and socioeconomic status (risk factors of VTE) of these women, we can stratify analyses on these factors.

For our analysis we will use SPSS for Windows, release 23.0.

WP5

Objectives

To assess changes in the incidence rates of VTE among women of reproductive age overall and by CHC-initiation/switching in Denmark between January 2012-January 2014 and February 2014-December 2015.

Study population

For each calendar year of the study period (1 January 2012 to 31 December 2015) we will identify women who were between 18 and 49 years old. Individuals with no previous record of VTE prior to study entry (from 2002 onwards) will be followed until they are recorded with a VTE, become 50 years of age, 31st of December 2015 or they migrate.

Analysis

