From segmented regression analysis (WP3), we will obtain information on a potential change in the proportion of initiators of each generation of CHC between January 2012-January 2014 and February 2014- December 2015. Since we have information about the prescription patterns among new users, we can assess whether the changes observed in the proportions of each generation is associated with changes in the incidence rate of VTE in women initiating oral contraceptive use.

Furthermore, we can study the changes in the incidence of VTE within users of different types

(and generations) of oral contraceptives. A change in this incidence over time, may indicate that certain preparations are prescribed to low/high risk individuals.

Analysis will be performed using Stata version 14 or higher.

WP7

Outline for the study report

The study report will combine the findings from all 6 work packages. Data from three countries will be used to report on the trends in first ever user prescribing in the two years preceding the relevant Commission Decision January 2012 – January 2014 and the period following the decision February 2014 – December 2015 . Furthermore, using different research strategies, we will report on the changes in the incidences of VTE in the different observation windows, separately for each country. The report will provide evidence regarding the necessity of the recommendation to use safer oral contraceptive preparations as it will show whether the implementation of the recommendation was successful and whether it actually affected the incidence of VTE in the target population.

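### Confounding by indication is ticked not applicable, and the WP6 VTE rates by CHC generation carry no patient-risk control, although the Decision steered both product and patient by VTE risk

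*Protocol*

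**What the plan says.** **Checklist.** Item "7.1.1. Does the protocol address confounding by indication if applicable" is ticked N/A, with no comment explaining that item. Item "10.4 Does the plan describe methods for adjusting for confounding" is ticked No, and so is "12.1.3 Residual/unmeasured confounding". The parent item, "7.1 Does the protocol describe how confounding will be addressed in the study", is ticked Yes with a pointer to stratification in section 9.2. The only comment under Section 7 of the checklist is "Ad 7.1 This is a descriptive analysis". Item 3.4 says measures of association are specified for WP4 to WP6.

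**What the Decision asked for (section 7).** It named the lowest-risk products and also told health care professionals that "CHC are contraindicated in the presence of one serious or multiple risk factors for VTE".

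**Analyses at issue (section 9.2).** WP4 and WP6 estimate VTE incidence in new users by type and generation, and both say "we can assess whether the changes observed in the proportions of each generation is associated with changes in the incidence rate of VTE". Both add that a change in incidence within a generation over time may mean that "certain preparations are prescribed to low/high risk individuals". Section 7 and WP7 say the report will show whether the recommendation actually affected VTE incidence.

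**Planned control.**
- Netherlands: the abstract commits to stratifying by age and socioeconomic status; WP4 in section 9.2 says only that this can be done.
- UK: WP6 stratifies the calendar-year rates by age, deprivation, BMI and smoking. The next paragraph, on window rates by type and generation, names no factor.
- Denmark and UK: the abstract compares age-standardised VTE rates with age-standardised initiations, overall rather than by generation. WP5 has a related age-standardised comparison; WP6 does not repeat it.

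**The concern.** If prescribers acted on both messages, the women starting each generation after the Decision differ in baseline VTE risk. A crude comparison of generations then mixes the product's effect with the selection of its users. Suppose higher-risk women who still start are steered to the lowest-risk products. The VTE rate of those products rises, their measured advantage shrinks, and the link sought in Objective 4 between generation shares and VTE rests on distorted rates.

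A threat that the protocol itself names as a possible reading of its results cannot be inapplicable to it. Calling the analysis descriptive does not settle the matter either, because Objective 4 seeks an association and WP7 promises a statement about effect.

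**Working it through.** The protocol gives no figure for the size of this bias. Its one expected event count, 480 Danish cases, reproduces (300 000 × 4 × 4/10 000 = 480), but the point does not rest on it.

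**Inputs from the protocol (risk table in the abstract).** Levonorgestrel, norethisterone or norgestimate: 5–7 per 10 000 per year, midpoint 6. Drospirenone, gestodene or desogestrel: 9–12, midpoint 10.5. Ratio of midpoints: 10.5/6 = 1.75.

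**Assumptions, not in the protocol.** One binary patient risk factor with risk ratio RR for VTE, and the share q of starters in each generation who carry it.

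**Step 1: bias in the crude generation ratio.** Crude ratio = 1.75 × [1 + q3(RR − 1)] / [1 + q2(RR − 1)], where q2 is the share in second-generation starters and q3 the share in third/newer-generation starters.

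| q2, q3 | RR | Crude ratio |
|---|---|---|
| 15%, 15% | any | 1.75 |
| 25%, 12% | 2 | 1.75 × 1.12/1.25 = 1.57 |
| 25%, 12% | 2.5 | 1.75 × 1.18/1.375 = 1.50 |
| 25%, 12% | 3 | 1.75 × 1.24/1.50 = 1.45 |
| 20%, 10% | 2, 3, 5 | 1.60, 1.50, 1.36 |
| 25%, 5% | 2, 3, 5 | 1.47, 1.28, 1.05 |

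With equal shares there is no bias. The bias grows with the gap in shares and with RR.

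**Step 2: the total initiator rate.** A product shift from 50/50 to 60/40 takes the mean rate from 0.5 × 6 + 0.5 × 10.5 = 8.25 to 0.6 × 6 + 0.4 × 10.5 = 7.80, a fall of 5.5%. With no product shift, a fall in the high-risk share from 20% to 15% at RR 2.5 gives 1.225/1.300, a fall of 5.8% (4.2% at RR 2, 7.1% at RR 3). These shifts were chosen for illustration. They show only that the total rate by itself is ambiguous.

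**Step 3: do the planned within-generation rates resolve it?** In Step 2 they do, in expectation. The pure product shift leaves 6 and 10.5 unchanged, while the pure risk-mix shift lowers both to 6 × 0.942 = 5.65 and 10.5 × 0.942 = 9.89.

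Under differential channelling they signal selection but do not remove it. Let both generations have a 15% share before, and 25% and 12% after, at RR 2.5. The second-generation rate goes from 6 to 6 × 1.375/1.225 = 6.73, and the third/newer rate from 10.5 to 10.5 × 1.18/1.225 = 10.11. The opposite movements hint at selection, but the later ratio is still 10.11/6.73 = 1.50. If the same channelling were present in both windows, the ratio would be biased in both and no trend would show.

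**The case against.** Four points on the other side carry weight.

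- A reader might infer from the two ticks that no adjustment is planned at all. The document does not support that. Item 7.1 is ticked Yes for stratification, the abstract commits the Dutch analyses to age and socioeconomic strata, and age standardisation is planned for Denmark and the UK. Nor is the descriptive comment a stated ground for item 10.4: it is attached to 7.1, and the comments under Section 10 are blank.
- A reader might also infer that the planned rates cannot separate product mix from patient selection. Step 3 shows that they can when the risk mix shifts uniformly, and the protocol states that reading itself. What remains is that the check is partial and informal.
- Fewer high-risk starters is partly what the Decision intended. For the before/after contrast, patient selection is part of the answer and not only a nuisance. This stands, and it means the unadjusted window contrast must stay in the report.
- Model specification commonly sits in a statistical analysis plan, which is not shown, and item 10.4 may simply be candid. That excuses the missing model detail. It does not excuse an N/A at 7.1.1 that contradicts section 7, WP4 and WP6. Nor does it explain why WP6 attaches its risk-factor strata to one set of rates and not to the set by generation.

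The shares and risk ratios are assumptions, and the protocol offers nothing to narrow them.

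**Conclusion.** The point holds in a limited form. The N/A at 7.1.1 is wrong on the protocol's own text. Planned control stops at stratification and age standardisation, and none of it is stated for the WP6 rates by window and type or generation. Under the assumed 25% and 12% shares, a true ratio of 1.75 would be read as 1.57 to 1.45 for risk ratios of 2 to 3, which is 10% to 17% too low (1.12/1.25 = 0.90; 1.24/1.50 = 0.83). Other assumed shares give anything from no bias to a ratio near 1.

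Two further inferences would go too far. Adding generation to an adjusted model does not isolate the part of the VTE change attributable to product mix unless no unmeasured confounding between generation and VTE remains, and the protocol gives no basis for that. Nor does the effect of UK adjustment for BMI and smoking bound the Dutch result: the populations differ, and so do the outcomes (Read-coded diagnoses against an anticoagulant proxy).

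This should be changed before analysis. It does not invalidate the design.

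**What to change.** 1. **WP6.** Report the generation and window VTE rate ratios both unadjusted and adjusted for age band, Townsend quintile, BMI and smoking. Use a Poisson model with a log person-time offset, or standardise to a fixed risk-factor mix. Collapse sparse cells where needed.
2. **WP4.** Do the same with age and socioeconomic status, and bring the wording in section 9.2 into line with the commitment in the abstract.
3. **Window contrast.** Present it with and without patient-factor adjustment, and say that the unadjusted version includes the intended effect of fewer high-risk starters.
4. **Checklist.** Correct items 7.1.1 and 10.4 once the text supports a Yes.
5. **Section 9.5.** Add residual confounding, especially for the Netherlands, where only age and socioeconomic status are named.
6. **Section 7 and WP7.** Limit the conclusion to an association between changes in CHC use and changes in VTE incidence.

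The cost is wording and a few extra models on variables already planned. Intervals will be somewhat wider and some strata sparse. How much wider cannot be said: the protocol gives no expected VTE count for UK new users and calls the Dutch one difficult to estimate.
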